Secondary Hypothesis 3B: Prehospital tranexamic acid as compared to placebo will attenuate trauma-induced pro-inflammatory changes and immunosuppression by reducing the early inflammatory cytokine response (GM-CSF, IFN- γ , IL-1 β , IL-2, IL-4, IL-5, IL-6, IL-8, IL-10 and TNF- α), HMGB1 levels and early inflammatory gene responses as measured by RT-PCR.

E.3.4. Secondary Aim#4: Determine whether different dosing regimens of tranexamic acid upon arrival in the hospital are associated with improvements in hyperfibrinolysis, markers of coagulopathy, clinical outcomes, platelet and leukocyte activation and the early inflammatory response.

Secondary Hypothesis 4A: Repeat dosing of 1 gram of tranexamic acid followed by 1 gram over approximately 8 hours after hospital arrival in patients who have already received 1 gram of prehospital tranexamic acid will lower the incidence of 12 hour (from arrival) hyperfibrinolysis (estimated percent lysis > 7.5%), coagulopathy (INR > 1.4) and improve r-TEG markers of coagulopathy, D-dimer levels, activated protein C levels and plasmin-antiplasmin complex levels as compared to standard dosing of tranexamic acid (1 gram over approximately 8 hours) or abbreviated dosing (no additional tranexamic acid).

Secondary Hypothesis 4B: Repeat dosing of 1 gram of tranexamic acid followed by 1 gram over approximately 8 hours after hospital arrival in patients who already received prehospital tranexamic acid will lower the incidence of 24 hour and 30 day mortality, acute lung injury, multiple organ failure and nosocomial infection as compared to standard dosing or abbreviated dosing.

Secondary Hypothesis 4C: Repeat dosing of 1 gram of tranexamic acid followed by 1 gram over approximately 8 hours after hospital arrival in patients who already received prehospital tranexamic acid will reduce 12 hour (from arrival) base deficit, 24 hour crystalloid requirements and 6 hour and 24 hour blood and blood component transfusion requirements (PRBC, FFP and platelets) as compared to standard dosing or abbreviated dosing.

Secondary Hypothesis 4D: Repeat dosing of 1 gram of tranexamic acid followed by 1 gram over approximately 8 hours after hospital arrival in patients who already received prehospital tranexamic acid will reduce 12 hour and 24 hour (from arrival) markers for platelet and leukocyte activation, plasmin

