I.2 Secondary Clinical Outcomes: Secondary clinical outcomes will include the incidence of hyperfibrinolysis (EPL > 7.5% by rapid-TEG analysis) upon arrival to the trauma bay within the first 6 hours, the incidence of acute traumatic coagulopathy (INR > 1.4), 24 hour mortality, acute lung injury, multiple organ failure, the development of nosocomial infection, early (24hr) seizures, in-hospital pulmonary embolism, presenting base deficit, 24 hour crystalloid requirements and 6 hour and 24 hour blood and blood component transfusion requirements (PRBC, FFP and platelets). *These same clinical outcomes will similarly be used for the randomized tranexamic acid dosage regimen comparison.*

I.3. Secondary Laboratory/Mechanistic Outcomes: All laboratory/mechanistic outcomes will be measured during the first 6 hours from trauma center arrival and at 12 and 24 hours (+/- 12 hours) out from injury. Those laboratory/mechanistic outcomes including flow cytometry which require fresh blood samples will be performed only at the University of Pittsburgh on a subset of patient samples unless participating centers have specific capabilities and following appropriate training for standardization. *These same laboratory/mechanistic outcomes will similarly be used for the randomized tranexamic acid dosage regimen comparison at 12 and 24 hours post-injury.*

I.4. Clinical Outcomes Methods/Definitions: All clinical outcomes will be prospectively evaluated for throughout ICU and hospital admission and the timing from the day of initial injury will be recorded for time-to-event statistical analysis.

I.4.1. 30 day and 24 hour mortality: 30 day mortality will be prospectively recorded from the day of trauma bay arrival. Over the first 24 hours we will document and record the time of death in hours. We suspect that patients enrolled will have a significant percentage of mortality that occurs in the first 24hrs.

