I.5. Laboratory/Mechanistic Outcome Methods/Definitions: All measurements will be performed within 6 hours of arrival and at 12 and 24 hours post injury (+/- 12 hours) for the randomized dosage regimen comparison. One more additional blood sample will be collected at 72 hours (\pm 12 hrs) for D-dimer, activated Protein C levels and plasmin-antiplasmin complexes measurements. Excluding r-TEG analysis and PT/ INR measurements, all blood and serum samples will be spun, stored and batched at their respective institution and delivered to the University of Pittsburgh where formal ELISA immunoassay measurements will be undertaken. Those laboratory/mechanistic outcomes including flow cytometry which require fresh blood samples will be performed only at the University of Pittsburgh on a subset of patient samples unless participating centers have specific capabilities and following appropriate training for standardization.

I.5.1. Coagulopathy and TEG parameters (Aim#2): To appropriately characterize differences in coagulopathy between tranexamic acid and placebo, in addition to r-TEG measurements of hyperfibrinolysis, presenting PT/ INR and additional TEG parameters will also be measured (ACT, r-value, k-time, α -angle, maximal amplitude, and G-values). All rapid TEG measurements will be performed within 6 hours of arrival and at 12 and 24 (+/- 12 hours) hours post injury. TEG analysis will be performed on a TEG[®] 5000 Thromboelastograph[®] Hemostasis Analyzer which will reside within the emergency department of each participating site. Standard laboratory INR will be drawn and measured at each institution within 6 hours of arrival and at 12 and 24 hours (+/- 12 hours). To further quantify the coagulopathy and hyperfibrinolysis post injury in these patients, D-dimer, activated Protein C levels and plasmin-antiplasmin complexes will be measured by ELISA plate assay. (ANIARA, USCN Life Science Inc., DRG International, Inc.) Plasmin-antiplasmin complexes may represent a more common, subclinical measurement of fibrinolytic activity that is not able to be assessed using standard TEG analysis, but elevated levels are associated with significantly worse outcome post injury and may be a marker than demonstrates the mechanism by which tranexamic acids has it beneficial effects.

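### The ±12 h tolerance makes the 12 h and 24 h laboratory windows overlap by half and lets the 12 h sample fall before or during the in-hospital regimen, which dilutes Aim 4's laboratory contrasts

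*Combined protocol and SAP*

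**What the plan says.** All references are to the combined protocol and SAP.

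- **I.3** times the laboratory and mechanistic draws "at 12 and 24 hours (+/- 12 hours) out from injury", besides an arrival sample in the first 6 hours. It adds that these outcomes will "similarly be used for the randomized tranexamic acid dosage regimen comparison at 12 and 24 hours post-injury".
- **I.5** repeats the rule and ties it to the regimens: measurements are taken "within 6 hours of arrival and at 12 and 24 hours post injury (+/- 12 hours) for the randomized dosage regimen comparison". **I.5.1** gives it again for rapid TEG, the source of the hyperfibrinolysis outcome: "within 6 hours of arrival and at 12 and 24 (+/- 12 hours) hours post injury".
- **E.3.4** counts from a different origin. Repeat dosing "will lower the incidence of 12 hour (from arrival) hyperfibrinolysis" (4A), "will reduce 12 hour (from arrival) base deficit, 24 hour crystalloid requirements and 6 hour and 24 hour blood and blood component transfusion requirements" (4C), and "will reduce 12 hour and 24 hour (from arrival) markers for platelet and leukocyte activation" (4D).
- **H.3.2** gives the regimens. After arrival sampling and eligibility verification, every patient receives a bolus (Bag B) and an infusion of about 8 hours (Bag C), each active or placebo according to arm. I found no deadline for starting either bag.
- **J.3** compares the regimens by chi-square, trend, regression and parametric or non-parametric tests, with no term for actual draw time. **N.2** and **N.3** do not list draw times or infusion start and stop times among the data elements.

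**The concern.** A tolerance as wide as the nominal time opens the 12 h window at the moment of injury, before enrolment. One draw at 18 h meets both labels. A draw 5 h after injury can be both the arrival sample and the 12 h sample. The regimens differ only in what Bags B and C contain, so a sample drawn before Bag B cannot differ by regimen. Pooled under the 12 h label, such samples pull the three-arm contrasts in hyperfibrinolysis, INR, D-dimer, plasmin-antiplasmin and cytokines toward zero. Samples drawn during Bag C reflect an incomplete regimen.

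The difference in time origin is a separate defect and would remain under a narrow tolerance. At stake is how a null laboratory result for Aim 4 would be read: as no difference between regimens, or as a product of when blood was taken.

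**Working it through.** **The plan's own figure.** The documents give no sample size or power for the Aim 4 laboratory comparison. The only sample size is 497 per arm for 30 day mortality (K.1). It reproduces: a two-sided pooled z-test of 0.0919, 0.0965 and 0.1003 against 0.16 gives power 0.9001, 0.8505 and 0.7996. It is used below only for the regimen arm size, 497/3 ≈ 166.

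**Windows (I.3, I.5).** 12 ± 12 = 0–24 h; 24 ± 12 = 12–36 h. The overlap is 12–24 h, which is 12/24 = 50% of each window.

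**Time origin (E.3.4 against I.3).** If arrival is 1 to 2 h after injury (assumed), 12 h from arrival is 13 to 14 h from injury.

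**Share of 12 h draws before the regimen.** Let the regimen start *s* hours after injury and the patient arrive at *a* hours. The documents give neither, so both are assumed, and draws are taken as evenly spread.

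| Spread of draws | Formula | s = 2 h | s = 4 h |
|---|---|---|---|
| From injury | s/24 | 2/24 = 8.3% | 4/24 = 16.7% |
| From arrival (a = 1 h for s = 2; a = 2 h for s = 4) | (s − a)/(24 − a) | 1/23 = 4.3% | 2/22 = 9.1% |

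A draw at exactly 12 h is never pre-regimen unless the start is delayed beyond 12 h.

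**Share of 12 h draws during the regimen.** A bolus of about 10 minutes plus 8 h is 8.17 h. From injury this is 8.17/24 = 34%; from arrival, 8.17/23 = 36% or 8.17/22 = 37%.

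**24 h draws.** The window opens at 12 h, so a draw can be mid-infusion only if s + 8.17 > 12, that is s > 3.83 h. With draws spread evenly from 12 to 36 h, the share is 0% at s = 2, (12.17 − 12)/24 = 0.7% at s = 4, and (14.17 − 12)/24 = 9% at s = 6. None precedes the regimen unless s > 12 h.

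**What the pre-regimen share could cost.** This takes a pairwise contrast of a continuous marker, 166 per regimen, all sampled, two-sided alpha 0.05, and no effect in pre-regimen draws. The difference with 80% power is (1.960 + 0.842) × √(2/165.67) = 0.308 SD. If a fraction *f* of draws is pre-regimen, power is about Φ(2.802 × (1 − f) − 1.960): 77% at f = 0.04, 73% at f = 0.08 and 64% at f = 0.17.

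**The case against.** A reader might infer that Aim 4's 12 h and 24 h hypotheses cannot be answered at all. The documents do not support that:

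- Hypothesis 4B (mortality, lung injury, organ failure, infection) and the transfusion and crystalloid parts of 4C do not use these samples.
- The 24 h draw is almost wholly post-infusion if the regimen starts within about 4 h of injury.
- Treatment and research staff are blinded (H.5.2, H.6), so there is no evident reason for draw timing to differ by arm. The expected harm is lost signal, with no evident bias toward one regimen.
- I.5 adds a draw at 72 h (±12 h, so 60–84 h) for D-dimer, activated protein C and plasmin-antiplasmin. It overlaps neither window, though it cannot stand in for a 12 h value.

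It is also tempting to discount every mid-infusion sample by a fixed fraction. Nothing in the documents supplies one. Standard and repeat dosing share the same Bag C and differ only in the Bag B bolus; if Bag B is given first, that difference has been delivered by mid-infusion. Hypothesis 4A asks about status at 12 h, which need not be after a completed regimen.

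Sites may well draw near the nominal times. N.4 mentions a Manual of Operations and section O mentions training in sample collection; neither is in the documents, so tighter operational timing is possible. Finally, the tolerance could be read as belonging to the 24 h draw only. The 12 h draw would then have no stated window, and the 24 h window would still open at 12 h.

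These points limit the harm. They do not remove the overlap, the admission of pre-regimen draws under the stated rule, or the two time origins.

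**Conclusion.** The point holds for the laboratory parts of 4A, 4C (base deficit) and 4D, chiefly at 12 h. The windows, their 12 h overlap and the conflict between injury and arrival follow from the text without assumption, reading the tolerance as applying to both draws. The stated rule permits a sample taken before Bag B to be analysed as the 12 h dosing outcome, and J.3 has nothing to correct for it.

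The size is an illustration. With a start 2 to 4 h after injury, 4–9% to 8–17% of 12 h draws would be pre-regimen, depending on whether draws spread evenly from an assumed arrival at 1 to 2 h or from injury. The second figure is an upper case, because it includes time before the patient reaches the trial centre. About a third would be mid-infusion, and I put no loss on those. Drawing near nominal times makes all of this smaller.

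The conclusion is diluted and blurred contrasts in one secondary aim. The primary outcome is unaffected. The change should still be made, because it is cheap and a null 12 h laboratory result would otherwise be hard to interpret.

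**What to change.** Amend I.3, I.5 (with I.5.1) and E.3.4 together:

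1. Use one time origin for the dosing-comparison draws: trauma-bay arrival, as the hypotheses already do.
2. Make the 12 h and 24 h windows non-overlapping, so that each draw carries one label. With symmetric windows, any tolerance below (24 − 12)/2 = 6 h achieves this and also keeps the 12 h window clear of the 0–6 h arrival window. The exact limits are for the investigators to choose.
3. Do not count the arrival sample, or any draw before Bag B, as the 12 h dosing sample. All arms receive a Bag B under blinding, so this exclusion should not depend on arm. State how patients who never start Bag B are handled.
4. Record actual draw times and the start and stop times of Bags B and C (add to N.3).
5. Add to J.3 an analysis using actual time since the start of the in-hospital regimen.

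I would not restrict the 12 h sample to draws after Bag C ends. That selects on events after randomisation, such as a delayed infusion, and discards on-treatment information that item 5 can use.

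The cost is wording, a few time fields, and some draws that are relabelled or leave the main laboratory comparison. No draws are added.

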I.4.2. Acute lung injury: Development of acute lung injury will be assessed utilizing the 1992 American-European Consensus Conference definition⁹⁰ which includes: 1) bilateral infiltrates on cxray, 2) a capillary wedge pressure < 18mmHg, and 3) Pao2/Fio2 ratio < 300 via blood gas analysis. In those patients without a Swan-Ganz catheter (vast majority) to determine capillary wedge pressure, the absence of signs of or clinical concern for elevated left sided atrial pressures will be used for the diagnosis. All patients who remain intubated beyond the first 24 hours post injury will be evaluated using blood gas analysis and cxray evaluation. Those patients who remain intubated at 48 hours thru 7 days will be reevaluated for this outcome at these time points. All time variables to the respective

outcome event will be determined from the day of initial injury for time-to-event analysis and multivariate Cox proportional hazard regression analysis.

I.4.3. Nosocomial infection: Infectious outcomes of interest will include ventilator associated pneumonia, blood stream infection and urinary tract infections. Surgical site infections and post-operative intra-abdominal collections will also be recorded but excluded as a principal secondary outcome event to reduce the confounding effects of operative interventions which not all patients require. The development of these nosocomial infections will be based upon positive culture evidence during hospital admission. Infections will be monitored until post injury day 30 or ICU discharge. Diagnosis of ventilator associated pneumonia requires a quantitative culture threshold of $\geq 10^4$ CFU/ml from broncho-alveolar lavage specimens in addition to standard x-ray and clinical criteria. Diagnosis of catheter-related blood stream infections requires positive peripheral cultures with an identical organism obtained from either a positive semi-quantitative culture (>15 CFU/segment), or positive quantitative culture ($>10^3$ CFU/segment) from a catheter segment specimen. Urinary tract infections required $> 10^5$ organisms/ml of urine. All time variables to the respective outcome event will be determined from the day of initial injury, while the time to the first nosocomial infection will be used in those patients with multiple infections for time-to-event analysis and multivariate Cox proportional hazard regression analysis.

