I.4.4. Multiple organ failure: Organ dysfunction will be evaluated via a well-validated scoring system referred to as the Denver Postinjury Multiple Organ Failure Score.⁹¹⁻⁹³ Patients who are never admitted to the ICU or those with a length of ICU stay of less than 48 hrs will be considered to have a Denver score of 0. A summary of the Denver score may be calculated by summing the worst scores of each of the individual systems over the course of the ICU stay. A summary Denver score > 3 will be classified as multiple organ failure (MOF). Scores will be determined daily up until post injury day 30 or ICU discharge. All time variables to the respective outcome event will be determined from the day of initial injury, for time-to-event analysis and multivariate Cox proportional hazard regression analysis.

I.4.5. Early seizures: Seizures will be prospectively monitored for over the first 24 hours from injury. Whether the seizures occurred post-operatively or in those patients who did not require operative intervention will be documented. Neurology consultation will be sought in those patients with seizure activity. Classification of seizure type and management will be based upon formal neurology consultation. Repeat occurrence and outcomes associated with seizure will similarly be documented.

I.4.6. In-hospital pulmonary embolism: Pulmonary embolism that occurs during the primary admission hospital stay will be documented for all enrolled patients. Radiographic confirmation via CT imaging, transthoracic or trans-esophageal echo, or ventilation/perfusion scanning will be required.

I.4.7. Blood and blood component transfusion and resuscitation requirements: 6 and 24-hour transfusion requirements for blood, fresh frozen plasma and platelet transfusion will be determined by recording the number of units transfused for each component from the time of trauma bay arrival. Transfusion components which are initiated will be considered transfused irrespective of completion. Similar determinations for crystalloid requirements (volume in cc's) over the first 24hrs of injury will occur.

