
J.2. Analysis of Prehospital Randomized Secondary Outcomes: Unless there is sufficient power (predetermined before the analysis is begun), the approach to analysis of secondary endpoints will generally be calculation of confidence limits on intervention group differences or model parameters rather than formal tests of significance at a specified critical level as the trial will not have sufficient power to detect difference in all of these outcomes. However, these comparisons will add to the knowledge of the benefits and risks of the interventions. Parametric and nonparametric comparisons will be applied according to normalcy. All tests used will be two-tailed tests at significance level (α) of 0.05. For prehospital randomized clinical outcomes we will use Chi-square with 95% confidence intervals for dichotomous outcomes and parametric or non-parametric testing for continuous variable with 95% confidence intervals. For prehospital randomized laboratory or exploratory outcomes we will use parametric or non-parametric testing for continuous variable with 95% confidence intervals.

J.3. Analysis for Second Stage In-hospital Randomized Dosage Regimens: Chi-square test will be able to test the effect of different tranexamic dosage regimens on hyperfibrinolysis. Similarly, chi-square will be used to detect any differences between dosage groups for 30 day mortality. To detect a trend in dosage response, test for trend will be implemented. As additional analysis and to account for site and to adjust for some important covariates, we will use logistic regression to test the effect of dosage on hyperfibrinolysis. Similarly Cox proportional hazards regression can be used for 30 day mortality. *For In-hospital randomized dosage regimen comparison for clinical outcomes* we will use Chi-square with 95% confidence intervals for dichotomous outcomes and parametric or non-parametric testing for continuous variable with 95% confidence intervals. *For In-hospital randomized dosage regimen comparison for laboratory or exploratory outcomes* we will use parametric or non-parametric testing for continuous variable with 95% confidence intervals.

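### I.4.3 ends infection monitoring at ICU discharge, which contradicts its own whole-admission definition and lets ICU stay influence the comparison of infection proportions

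*Combined protocol and SAP*

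**What the plan says.** The combined protocol and SAP gives three statements about when infections count.

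- Section I.4, for every clinical outcome: "All clinical outcomes will be prospectively evaluated for throughout ICU and hospital admission".
- Section I.4.3, definition: "The development of these nosocomial infections will be based upon positive culture evidence during hospital admission".
- Section I.4.3, next sentence: "Infections will be monitored until post injury day 30 or ICU discharge". It does not say whether the earlier or the later of the two applies.

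The components are stated as: "Infectious outcomes of interest will include ventilator associated pneumonia, blood stream infection and urinary tract infections". I.4.3 has no rule for a patient who never enters the ICU.

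Two neighbouring sections are useful for comparison. I.4.4 uses the same pair of end points for daily organ failure scoring and does provide for the rest of the population: "Patients who are never admitted to the ICU or those with a length of ICU stay of less than 48 hrs" are assigned a Denver score of 0. I.4.6 uses a whole-stay window: "Pulmonary embolism that occurs during the primary admission hospital stay will be documented for all enrolled patients".

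Two analyses are planned. J.2 states: "For prehospital randomized clinical outcomes we will use Chi-square with 95% confidence intervals for dichotomous outcomes". I.4.3 adds a time-to-first-infection analysis with Cox regression, but gives no censoring or competing-event rule for ICU discharge or death.

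**The concern.** A coordinator who follows the specific monitoring sentence stops looking at ICU discharge. One who follows I.4 or the definition continues on the ward. Sites could therefore collect different outcomes under one name.

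If the ICU cut-off governs, the length of observation is itself a post-randomization result. Entry can rest on tachycardia alone (H.2.1), and I.4.4 foresees patients with no ICU stay or a short one, so observation times will vary widely. The J.2 comparison makes no allowance for time observed. If one arm leaves the ICU sooner, it is watched for less time and shows fewer infections even when the infection rate is the same. If one arm stays longer, the reverse happens.

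Nosocomial infection appears in Aim 1, in Secondary Hypotheses 2A and 4B, in the dosage-regimen comparison (I.2), in the DSMB charter's list of monitored events and in Table 6 of Appendix 4. An ascertainment artefact would carry into each of these.

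**Working it through.** **Step 1. Which reading is natural?** Set I.4.3 beside I.4.4. Both end at day 30 or ICU discharge. In I.4.4 the summary score covers the ICU stay, so ICU discharge must end scoring and the earlier event applies. The same words in I.4.3 are most naturally read the same way. That cut-off suits an ICU score, but it does not suit an outcome defined as "will be based upon positive culture evidence during hospital admission". I.4.6 shows how a whole-stay window for all enrolled patients is written in this protocol.

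**Step 2. Size of the effect on the proportion.** The documents give no infection rate, ICU share or ICU stay, so there is no stated figure to reproduce, and the inputs below are assumptions.

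- Arm size 497 and two-sided alpha 0.05: from K.1. As a check, the power formula below gives 0.900, 0.8505 and 0.7996 for the K.1 rows stated as 0.90, 0.85 and 0.80.
- ICU share s = 0.7 (range 0.5 to 0.9): assumed.
- Infection hazard h = 0.02 per day, equal in both arms (range 0.01 to 0.03): assumed.
- ICU stay exponential with mean m days: assumed.

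Risk of an infection being seen before the earlier of ICU discharge and day 30:

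risk = s × h / (h + 1/m) × [1 − exp(−30(h + 1/m))]

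- m = 6: 0.7 × 0.02/0.18667 × (1 − e^−5.6) = 0.0747
- m = 5: 0.7 × 0.02/0.22 × (1 − e^−6.6) = 0.0635
- m = 4: 0.7 × 0.02/0.27 × (1 − e^−8.1) = 0.0518

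Risk ratios with no true effect on infection: 0.0635/0.0747 = 0.85 and 0.0518/0.0747 = 0.69.

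Probability that a pooled z-test (equivalent to the uncorrected chi-square) rejects in favour of the shorter-stay arm:

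Φ{[d − 1.96 √(2p̄(1−p̄)/497)] / √([p0(1−p0) + p1(1−p1)]/497)}

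For 6 versus 4 days, d = 0.0229 and both standard errors are 0.0154, which gives 0.316. For 6 versus 5 days it is 0.103. The nominal rate in that one direction is 2.5%, half of the two-sided 5%.

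| Mean ICU stay, days | Risk ratio, s and h over their ranges | Rejection in that direction |
|---|---|---|
| 6 vs 5 | 0.84–0.86 | 6–15% |
| 6 vs 4 | 0.68–0.70 | 15–51% |
| 10 vs 7 | 0.74–0.76 | 15–51% |

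**Step 3. The other window and the other analysis.** Simulation with 300 trials per scenario, s = 0.7, ICU hazard 2% per day, a mean ward stay of 6 days in the longer-ICU-stay arm and in never-ICU patients, and mean total hospital stay held equal between arms.

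- ICU-limited window, 6 vs 4 days, ward hazard also 2%: 7.5% vs 5.2%; two-sided chi-square rejects in 32% of trials.
- Whole-admission window, same scenario: 17.2% vs 17.1%; rejects in about 6%.
- Cox among ICU patients censored at ICU discharge, across all scenarios run: mean log hazard ratio between −0.02 and 0.01; rejection 3–5%. There is no artefact when discharge is unrelated to infection risk.
- Share of in-hospital infections outside the ICU-limited window, 6 vs 4 days: 63%, 48% and 32% for ward hazards of 2%, 1% and 0.5% per day.

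One caution: with a ward hazard of 0.5%, the whole-admission window gives 10.0% vs 8.5% and rejects in 16% of trials. There, earlier transfer to a lower-risk setting really does lower infections, so that difference is not an ascertainment artefact.

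**The case against.** The strongest reply is that this is an unresolved contradiction, not a settled design. I.4 and the definition both point to the whole admission, and the monitoring sentence never says whichever is earlier. That stands. A reader might infer that ward and never-ICU infections will certainly be missed, or that the infection objective goes unanswered for the randomized population. The documents do not establish either: on the hospital-admission reading the objective is answered, and on the ICU reading a narrower outcome is.

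A reader might also infer that any treatment effect on ICU stay must appear as an infection effect in every analysis. The documents do not support that. I.4.3 plans a Cox analysis too, and Step 3 shows no artefact there unless discharge is related to infection risk, which is plausible but not shown.

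Other points that stand:

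- J.2 generally reports confidence limits for secondary outcomes, with formal tests only where power is sufficient. This limits the relevance of the rejection rates. It does not protect the estimate or its interval, which carry the same shift.
- I.4.4 gives no frequency of never-ICU patients, and no hypothesis states that tranexamic acid changes ICU stay. The link through less organ failure and transfusion is an inference.
- Ventilator-associated pneumonia needs ventilation, and the bloodstream criterion given is catheter-related, so the ward loss may fall largely on urinary infections. Clinical pneumonia and sepsis are noted from discharge summaries (I.4.10), but that is not the culture-defined outcome.
- A window ending at hospital discharge still ends at an event that treatment may change. It reduces the dependence on length of stay without removing it.

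**Conclusion.** The monitoring sentence in I.4.3 conflicts with the definition beside it and with I.4, and it should be changed. Under the whichever-first reading, which the parallel wording in I.4.4 makes the natural one, the rule leaves out ward infections after ICU discharge, gives never-ICU patients no window, and makes the J.2 proportion comparison reflect differences in ICU stay as well as infection.

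The size is conditional. With equal infection hazards, a one-day difference in mean ICU stay (6 vs 5) gives a risk ratio of about 0.85, and a two-day difference (6 vs 4) about 0.69. These ratios change little over the assumed ICU shares and hazards; they depend mainly on the ICU-stay difference, for which the documents give no figure. If the arms have equal ICU stays, the artefact disappears and only the incomplete capture remains.

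The point concerns one secondary outcome that the DSMB also monitors. The primary outcome and the sample size are unaffected.

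**What to change.** Replace the monitoring sentence in I.4.3 with wording such as: ventilator-associated pneumonia, bloodstream and urinary infections will be recorded for all enrolled patients until post-injury day 30 or hospital discharge, whichever is first, irrespective of ICU admission.

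Then:

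- use that window for both the J.2 proportion and the time-to-first-infection analysis, so that never-ICU patients count in the denominator with a real observation period;
- treat death and hospital discharge before day 30 as competing events in the time-to-event analysis, because the window still ends at a post-randomization event;
- keep the ICU-only count as a descriptive supplement.

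Cost: one sentence in I.4.3, a short addition on competing events, and a revised case report form instruction. Coordinators must review existing culture results for ward days as well. No new cultures are needed, and infectious outcomes and length of stay are already in-hospital data elements (N.3).
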